3.5.2. Visit Schedule

A summary of the visit schedule and assessments is presented in [Table 2](#).

Table 2: Visit Schedule and Assessments

| | Screening Day -21 to -1 | Induction Weeks 1-3 | Rest Weeks 4-5 | Challenge Week 6 | EOS | Rechallenge |
|--|----------------------------|------------------------|-------------------|---------------------|-----|-------------|
| Informed consent | X | | | | | |
| Demographics | X | | | | | |
| Inclusion/Exclusion | X | | | | | |
| Medical history | X | | | | | |
| UPT | | X ^a | | | X | |
| Randomization | | X ^a | | | | |
| Study treatment applications and/or removals | | X | X ^b | X | | X |
| Evaluations | | X | X ^c | X | | X |
| Make-up applications (if applicable) | | X | | | | |
| Concomitant medications | X | X | X | X | X | X |
| Adverse events | | X | X | X | X | X |

a: Day 1 only

b: Day 1 of Week 4, removal/evaluation of last Induction patch.

c: 48-72 (± 4) hour evaluation of MU patch (if applicable).

Note: The visit schedule may be revised if necessary.

3.5.3. Background Information

Date of birth, gender, race, Fitzpatrick skin type (see [Table 1](#)), and a significant medical history of each subject will be recorded at Screening.

3.5.4. Efficacy Assessments

No efficacy will be assessed in this study.

3.5.5. Safety Assessments

3.5.5.1. Local Tolerability Assessments

Assessment of the patch sites will be conducted by a trained evaluator once at Baseline (Day 1), 9 times during the Induction Phase, 4 times during the Challenge Phase and, if applicable, 4 times during Rechallenge. The trained evaluator will assign a grade to each site ([Table 3](#)). There will be a main evaluator for the study; a backup evaluator will also be assigned in the event that an emergency occurs and the main evaluator is unable to attend the study visit. For the purpose of statistical analysis only, each grade will correspond to a score. The following symbols and their respective numerical equivalents (see [Table 3](#)) will be used to express the response observed at the time of examination (see [Table 4](#)):

Table 3: Response Symbols and Numerical Equivalents

| Grade | Score* | Definition |
|--------------|---------------|---|
| 0 | 0 | No evidence of irritation |
| 1 | 1 | Minimal erythema; barely perceptible |
| 2 | 2 | Definite erythema, readily visible; or minimal edema; or minimal papular response |
| 3 | 3 | Erythema and papules |
| 4 | 3 | Definite edema |
| 5 | 3 | Erythema, edema, and papules |
| 6 | 3 | Vesicular eruption |
| 7 | 3 | Strong reaction spreading beyond test site |

*Scores are utilized only during the statistical analysis process of the study. Grades will be conducted throughout the study by the trained evaluator.

Table 4: Effects on Superficial Layers of Skin

| Grade | Score* | Response |
|-------|--------|--|
| A | 0 | Slight glazed appearance |
| C | 1 | Marked glazing |
| E | 2 | Glazing with peeling and cracking |
| F | 3 | Glazing with fissures |
| G | 3 | Film of dried serous exudate covering all or portion of the patch site |
| H | 3 | Small petechial erosions and/or scabs |

*Scores are utilized only during the statistical analysis process of the study. Grades will be conducted throughout the study by the trained evaluator.

Other notations (see [Table 5](#)) may be made in place of a score to designate particular circumstances preventing the assignment of a score or in addition to a score to identify damage to the epidermis and/or spreading of a reaction beyond the patch site.

The actual patch test grades are a combination of a numerical ([Table 3](#)) and letter ([Table 4](#)) grades consistent with the definitions given in the grading scales. However, in order to determine discontinuation of a patch site (grade > 3) and to perform statistical analyses, grades containing letter grades have to be converted to numerical equivalents. These are converted as follows: A=0, C=1, E=2 and F, G, and H =3. These equivalents are considered additive to any numerical score (e.g., 2C=2+1=3), in this case the patch site would be discontinued.

Table 5: Other Notations

| Notation | Definition |
|----------|---|
| X | Subject absent |
| B | Burning or stinging sensation |
| PD | Patch dislodged |
| NA | Patch not applied |
| NP | No patch due to limiting irritation |
| I | Itching |
| D | Damage of the epidermis: oozing, crusting, and/or superficial erosions |
| p | Papular response |
| pv | Papulovesicular response |
| S | Spreading of reaction beyond patch site (i.e., reaction where study material did not come in contact with skin) |
| T | Tape related reaction |

Details regarding the statistical analysis of the cumulative irritation scores are provided in [Section 4.6](#).

3.5.6. Criteria for Changing the Application Site or Conditions

A grade of 3 or higher to a study product (using [Table 3](#) and [Table 4](#)) observed at the first or second reading of the Induction Phase would indicate the subject to be pre-sensitized, and application of the product in question would be discontinued.

After the second reading of the Induction Phase, reactions graded 3 or higher (using [Table 3](#) or [Table 4](#)) require that the investigational product be applied to a naïve site under occlusive conditions. Such a change of application site may occur no more than twice during the Induction Phase for a particular product, after which applications of the product will be discontinued for that subject for the remainder of the study. Subjects requiring site changes due to irritancy in the Induction Phase will be considered evaluable for sensitization, provided that they receive a total of no fewer than 9 applications of the product.

No more than 2 changes for a given product will occur, whether the changes are to a new site under occlusive conditions (first move) or a new site under semi-occlusive conditions (second move).

Occlusive patch conditions include a Webril® cotton patch surrounded with Blenderm tape and covered with paper tape. There is no air flow under the patch. Semi-occlusive patch conditions include a Webril® cotton patch covered with paper tape, to allow air flow under the patch itself.

The 3-week period of continuous patch contact during the Induction Phase frequently results in tape-related irritation that is exacerbated by warm weather, but which occurs among some individuals irrespective of the season. Since adhesive tape is an integral part of the test article, tape-related irritation at the site will be documented as an application site reaction using the symbol “T” from [Table 5](#). Severe tape-related irritation will require a change of application site. Mild and moderate tape related reactions will not require of a change of application site. If all sites are experiencing tape reactions, the patch sites will be discontinued and a not patched (NP) symbol will be recorded for the remainder of the study. The subject will be discontinued from the study. An AE will be recorded in order to follow through to resolution of the tape related reaction.

3.6. Adverse Events

3.6.1. Method of Determining Adverse Events

Safety assessments will include recording AEs reported spontaneously by the subject or collected by the Investigator. AEs will be recorded at each visit throughout the study on the appropriate CRF. Every attempt should be made to describe the AE in terms of a diagnosis. If a clear diagnosis has been made, individual signs and symptoms will not be recorded unless they represent atypical or extreme manifestations of the diagnosis, in which case they should be reported as separate events.

Subjects should be asked whether, since the time of the last observation or visit, they had any of the following:

- Experience any changes in well-being;
- Used any new medications;

- Changed medication regimens (both prescription and OTC); and/or
- Were admitted to a hospital or had any accidents.

All questions should be of a general nature and should not suggest symptoms.

When an AE is suspected, all relevant evaluations will be carried out and appropriate treatment provided. Additional follow-up will be done as necessary ([Section 3.6.4](#)) and recorded in the subject's source documents, and the results will be provided to the Sponsor.

For AE definitions and reporting requirements refer to [Section 3.6.2](#) and [Section 3.6.3](#).

Note: Any observed response which can be denoted using the irritation criteria summarized in [Table 3](#) and [Table 4](#) will not be considered an AE. Likewise, any tape-related irritation will only be noted as an AE when all patches are discontinued due to tape reaction around all sites (see [Section 3.6.6](#)).

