3.6.2. Adverse Event Definitions

3.6.2.1. Adverse Events

Information about all local and systemic AEs, whether volunteered by the subject, discovered by Investigator questioning, or detected through other means, will be collected and recorded on the AE CRF and followed as appropriate.

An AE is defined as any untoward medical occurrence in a patient or clinical investigation subject administered a pharmaceutical product (or cosmetic product), which does not necessarily have a causal relationship with this treatment. An AE can therefore, be any unfavorable and unintended sign, symptom, or disease temporally associated with the use of a medicinal investigational product, whether or not considered related to the medicinal investigational product.

Adverse Events will be coded using the Medical Dictionary for Regulatory Activities (MedDRA).

Medical conditions/diseases present before starting study treatment are considered AEs only if they worsen after starting study treatment (any procedures specified in the protocol). Any AEs occurring before starting study treatment but after signing the ICF are recorded on the Medical History/Current Medical Conditions CRF.

To the extent possible, each AE will also be described by:

1. its duration (start and end dates),
2. the severity grade (mild, moderate, severe)
3. its relationship to the study drug,
4. the action(s) taken, and
5. as relevant, the outcome.

Note: Any observed response which can be denoted using the irritation criteria summarized in [Table 3](#) and [Table 4](#) will not be considered an AE. Likewise, any tape-related irritation will not be noted as an AE.

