3.6.2.4. Relationship of Adverse Events to Study Treatments

The Investigator is to classify the drug relationship of an AE according to the definitions outlined in [Table 6](#).

Table 6: Relationship of AE to Study Drug

| Association | Definition |
|-------------|--|
| Not related | (1) the existence of a clear alternative explanation (e.g., mechanical bleeding at surgical site) or (2) non-plausibility, e.g., the subject is struck by an automobile or cancer developing a few days after drug administration. |
| Unlikely | There is no medical evidence to suggest that the AE may be related to study drug usage, or there is another more probable medical explanation. |
| Possible | There is medical evidence to suggest that there is a reasonable possibility that the AE may be related to study drug usage. However, other medical explanations cannot be excluded as a possible cause. |
| Probable | There is strong medical evidence to suggest that the AE is related to study drug usage. |
| Definite | A clinical event, including laboratory test abnormality (if applicable), in which there is no uncertainty in its relationship to test drug (e.g., positive Rechallenge). |

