3.6.4. Adverse Event Follow-up

Any ongoing AE at the time of study completion or withdrawal will be followed until the AE is resolved or the subject is referred to his/her own PMD. The Investigator and the Sponsor will decide if longer follow-up is appropriate on a case-by-case basis. Subjects who experience any clinically significant AE will remain under medical supervision until the Investigator or the Sponsor's Medical Monitor deems the AE to be resolved, stabilized, or no longer serious enough to warrant follow-up.

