3.6.6. Expected Adverse Events

Any observed response in the patch test area that can be denoted using the irritation criteria summarized in [Table 3](#) and [Table 4](#) will not be considered an AE.

Tape related reactions will only be recorded as AEs when the subject is discontinued due to tape reaction around all sites. When 1 or 2 sites are experiencing severe tape related reactions, the application site will be stopped and the subject will continue on the study. This will be noted in the database as "T" as indicated in [Table 5](#) and will be considered an expected AE. When all application sites are experiencing tape reaction, the subject is discontinued and therefore be recorded as an AE. The subject will be followed up through resolution.

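### The AE exclusion for graded skin reactions has no exception for seriousness or confirmed sensitization, and the protocol gives conflicting rules on recording tape irritation as an AE

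*Combined protocol and SAP*

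**What the plan says.** **Graded reactions.** Section 3.6.1 states that a response the irritation criteria of Tables 3 and 4 can describe "will not be considered an AE. Likewise, any tape-related irritation will only be noted as an AE when all patches are discontinued" because of tape reactions around all sites. Section 3.6.2.1 repeats the exclusion inside the AE definition. Section 3.6.6 repeats it for the patch test area.

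**SAEs and follow-up.** Section 3.6.2.2 defines an SAE as an AE that meets one of the listed seriousness criteria. The 24-hour duty in sections 3.6.3, 3.7.2 and 3.7.3 attaches to SAEs. Follow-up attaches to AEs: "Any ongoing AE at the time of study completion or withdrawal will be followed until the AE is resolved" or the subject is referred to a personal physician (3.6.4).

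**Sensitization.** Section 4.6.2 treats a Table 3 response of 3 or greater that recurs at Rechallenge, at least as severe as at Challenge, as indicating sensitization. It also requires a narrative with the Investigator's opinion.

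**Tape irritation.**
- 3.6.2.1: "any tape-related irritation will not be noted as an AE".
- 3.5.6, when all sites react and the subject is discontinued: "An AE will be recorded in order to follow through to resolution of the tape related reaction".
- 3.6.6, opening rule: "Tape related reactions will only be recorded as AEs when the subject is discontinued due to tape reaction around all sites".
- 3.6.6, next sentences: a severe reaction at one or two sites is noted as T and "will be considered an expected AE".

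**The concern.** Keeping routine patch grades out of the AE tables is reasonable, because those grades are the study's endpoint data. The difficulty is that the exclusion has no upper limit. Table 3 extends to vesicles and to strong reactions that reach past the test site, and Table 4 extends to erosions and scabs. Confirmed sensitization is itself defined by a Table 3 grade, so it always falls inside the exclusion.

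AE status decides several things in this protocol: whether duration, severity, relationship, action taken and outcome are recorded (3.6.2.1), whether an event is followed to resolution (3.6.4), and whether it can become an SAE with expedited reporting. Safety assessed through AEs is a stated aim in section 2. The separate SAP promised in section 4.1 could change how AEs are tabulated, but it could not restore AE details that were never collected.

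The tape rules raise a different question: AE counts would depend on which section site staff followed.

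**Working it through.** No plan figure bears on this point, so the check is mainly a comparison of texts. The nearest number is the 1.5% bound in section 4.2. It reproduces as a one-sided exact bound for 0 of 200: 1 − 0.05^(1/200) = 1.487%. Nothing below depends on it.

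**Step 1: is confirmed sensitization inside the exclusion?**
- 4.6.2 requires a Table 3 response of 3 or greater at Rechallenge.
- 3.6.1, 3.6.2.1 and 3.6.6 exclude any response that Tables 3 and 4 can describe.
- So every confirmed case rests on an excluded response. None of the three sections makes an exception for severity, seriousness or confirmation.

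**Step 2: does this carry over to SAEs?**
- Under 3.6.2.2 an event must be an AE before it can be an SAE.
- A graded reaction is not an AE (step 1).
- Read literally, a graded local reaction that met a seriousness criterion is therefore not an SAE, and the 24-hour duty does not attach to it.

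**Step 3: does anything else require follow-up?**
- Scheduled Challenge readings end at 72 hours after removal, with a possible reading at 96 hours for scores of 3 or higher. Rechallenge readings end at 72 hours (3.5.1).
- Beyond that, the duty in 3.6.4 covers AEs. Section 3.5.6 shows that the protocol uses AE status for this purpose, since it records an all-site tape reaction as an AE so that it is followed to resolution. No equivalent is stated for a confirmed sensitization reaction.

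**Step 4: illustration of size (assumed counts).** The documents give no expected number of confirmed cases. Out of 200 evaluable subjects:
- 1/200 = 0.5%
- 2/200 = 1.0%
- 3/200 = 1.5%

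All would appear in the sensitization results. The text requires none of them to be recorded as AEs. The last value equals the section 4.2 figure only because the rule of three gives 3/200; the two are unrelated.

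**Step 5: tape rules by situation.**

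| Situation | 3.6.2.1 | 3.5.6 | 3.6.1 | 3.6.6 |
|---|---|---|---|---|
| All sites react, subject discontinued | Not an AE | AE | AE | AE |
| One or two sites, severe | Not an AE | Site reaction coded T | Not an AE | Not an AE by its first rule; expected AE by its next |
| One or two sites, mild or moderate | Not an AE | Site reaction coded T | Not an AE | Not an AE |

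The sections conflict in the first two rows. Section 4.3 counts AEs in all treated subjects, and 4.6.3 counts each subject once. With at least 200 treated, each affected subject can move overall AE incidence by at most 1/200 = 0.5 percentage points.

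The handling of a severe tape reaction also differs: 3.5.6 calls for a change of site, while 3.6.6 says the site is stopped. These two statements must be reconciled as well.

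**The case against.** The strongest reply is that the trial does not overlook sensitization. It is the primary objective. Section 4.6 is headed as the safety evaluation and treats irritancy, sensitization and AEs as three parts. Challenge and Rechallenge reactions receive narratives, and sections 4.1 and 4.6.2 treat a single confirmed case as a signal. Keeping endpoint events out of the AE tables avoids double counting. All of this stands. A reader might infer that the study could hide a sensitizing product, and the documents do not support that.

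Second, the documents never discuss a graded reaction that needs hospital care. Tables 3 and 4 describe skin appearance, not hospital admission or systemic illness. Section 3.6.1 has staff ask about admissions, and 3.6.2.2 allows medical judgment on important events. Section 3.7.2 lists death separately from SAEs, so a death would be reportable in any case. A careful investigator might well report such a reaction. This limits the point to what the text says when read literally; it does not supply the missing exception.

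Third, Table 6 illustrates a definite relationship as one where "there is no uncertainty in its relationship to test drug (e.g., positive Rechallenge". It is tempting to call this a direct contradiction of the exclusion. It is only suggestive: the row reads as a general causality definition, and rechallenge is also a general causality term.

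Fourth, most of the tape text agrees. Sections 3.5.6, 3.6.1 and the first rule of 3.6.6 coincide, 3.6.2.1 stands apart, and the expected-AE phrase may be loose drafting. That makes the repair easy, but staff still have incompatible instructions.

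**Conclusion.** The point holds as a gap in AE and SAE recording, follow-up and expedited reporting. It rests on a literal reading of the exclusion in 3.6.1, 3.6.2.1 and 3.6.6 together with the SAE definition in 3.6.2.2. Because the exclusion is an explicit rule, this is more than missing detail.

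No rate can be attached to the gap from the documents. The 0.5% to 1.5% range reflects assumed counts only. A reader might infer that the AE tables would show no related skin events at all. That does not follow, because the exclusion names Tables 3 and 4 only: Table 5 findings such as itching or burning, and systemic features, could still be AEs.

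The tape conflict is real but separate. It affects AE counts and has no bearing on whether sensitization is detected.

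**What to change.** - Keep routine grades out of the AE tables. In 3.6.1, 3.6.2.1 and 3.6.6, state that the exclusion does not apply to a graded reaction that meets a seriousness criterion or is confirmed as sensitization. Such a reaction is then recorded, followed and reported as an AE, or as an SAE where a criterion is met.
- Reconcile 3.5.6, 3.6.1, 3.6.2.1 and 3.6.6 to one rule for when tape irritation is recorded as an AE, and use the same wording in each.
- Reconcile the statements in 3.5.6 and 3.6.6 on what happens to a site with a severe tape reaction.

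The cost is protocol wording and a few more AE records. The small downside is that confirmed reactions will appear in both the sensitization and AE outputs, which a footnote can explain.

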3.6.2. Adverse Event Definitions

3.6.2.1. Adverse Events

Information about all local and systemic AEs, whether volunteered by the subject, discovered by Investigator questioning, or detected through other means, will be collected and recorded on the AE CRF and followed as appropriate.

An AE is defined as any untoward medical occurrence in a patient or clinical investigation subject administered a pharmaceutical product (or cosmetic product), which does not necessarily have a causal relationship with this treatment. An AE can therefore, be any unfavorable and unintended sign, symptom, or disease temporally associated with the use of a medicinal investigational product, whether or not considered related to the medicinal investigational product.

Adverse Events will be coded using the Medical Dictionary for Regulatory Activities (MedDRA).

Medical conditions/diseases present before starting study treatment are considered AEs only if they worsen after starting study treatment (any procedures specified in the protocol). Any AEs occurring before starting study treatment but after signing the ICF are recorded on the Medical History/Current Medical Conditions CRF.

To the extent possible, each AE will also be described by:

1. its duration (start and end dates),
2. the severity grade (mild, moderate, severe)
3. its relationship to the study drug,
4. the action(s) taken, and
5. as relevant, the outcome.

Note: Any observed response which can be denoted using the irritation criteria summarized in [Table 3](#) and [Table 4](#) will not be considered an AE. Likewise, any tape-related irritation will not be noted as an AE.

3.6.2.2. Serious Adverse Events

A “SAE” is any AE that:

- Results in death;
- Is life-threatening (Note: the term “life-threatening” refers to any AE that, as it occurs, puts the subject at immediate risk of death. It does not refer to an AE that hypothetically might have caused death if it were more severe).
- Results in hospitalization or prolongation of current hospitalization (not including hospitalization for a pre-existing condition that has not increased in severity or frequency from the subject’s underlying medical condition prior to entry into the study).
- Is a congenital anomaly/birth defect in the offspring of a subject.
- Is another serious (important medical events) event.
- Results in persistent or significant disability/incapacity.

(Note: Important medical events may not be immediately life-threatening or result in death or hospitalization but may be considered serious when, based on the appropriate medical judgment, they may jeopardize the subject or require medical or surgical intervention to prevent one of the outcomes listed above. Examples of such medical events include allergic bronchospasm requiring intensive treatment in an emergency room or at home; blood dyscrasias or convulsions that do not result in inpatient hospitalization; or development of drug dependency or drug abuse.)

